4.6.2 Criteria for Stopping the Study

If the Sponsor, Investigator, clinical monitor, or FDA officials discover conditions during the study that indicate that the study or a study site should be terminated, this action may be taken after appropriate consultation between the Sponsor, Investigator, and clinical monitor.

5.0 STUDY POPULATION

Prospective approval of protocol deviations to recruitment and enrollment criteria, also known as protocol waivers or exemptions, is not permitted.

5.1 Inclusion Criteria

Participants are eligible to be included in the study only if all of the following criteria apply:

1. Provision of signed and dated, written informed consent prior to any study specific procedures.
2. Healthy male and/or female participants aged 18 to 55 years, inclusive.
3. A body mass index between 18.0 to 30.0 kg/m², inclusive, and a minimum body weight of 50 kg.
4. Females must be of nonchildbearing potential, must not be lactating, must have a negative serum pregnancy test at the Screening Visit, and must have a negative urine pregnancy test on admission to the study site CRU. The nonchildbearing potential of the female participant will be confirmed at the Screening Visit by fulfilling 1 of the following criteria (see [Section 10.4.1](#) for additional information):
 - Postmenopausal defined as amenorrhea for at least 12 months following cessation of all exogenous hormonal treatments and with follicle stimulating hormone (FSH) levels in the laboratory defined postmenopausal range.
 - Documentation of irreversible surgical sterilization by hysterectomy, bilateral oophorectomy or bilateral salpingectomy but not tubal ligation.
5. Male participants should be willing to use double barrier contraception, i.e., condoms and spermicide, from the day of dosing until at least 90 days after dosing with the study treatment (see [Section 10.4.2](#) for additional information).
6. Male participants must agree not to donate sperm from the day of dosing until at least 90 days after dosing with the study treatment.
7. Considered generally healthy upon completion of medical history, physical examination, vital sign measurements, ECG, and clinical laboratory test results in the opinion of an Investigator at Screening and Admission/Day -1.
8. Must agree to abstain from alcohol intake 48 hours before administration of the study treatment, during the confinement period of the study until after the final Follow-up/EOS Visit.
9. Able to comply with the protocol and attend all scheduled visits.

5.2 Exclusion Criteria

Participants are excluded from the study if any of the following criteria apply:

1. History of any clinically important disease or disorder which, in the opinion of an Investigator, may either put the participant at risk because of participation in the study, or influence the results or the participant's ability to participate in the study.
2. History or presence of gastrointestinal, hepatic or renal disease or any other condition known to interfere with absorption, distribution, metabolism or excretion of drugs.
3. Estimated glomerular filtration rate $<90 \text{ mL/min/1.73 m}^2$ based on Modification of Diet and Renal Disease formula during Screening and on Admission/Day -1 ([Table 6](#)).
4. Any current active infections, including localized infections, or any recent history (within 1 week prior to study treatment administration) of active infections (including severe acute respiratory syndrome coronavirus 2 [SARS-CoV-2]), cough or fever, or a history of recurrent or chronic infections.
5. Administration of any vaccine (live and inactivated [e.g., inactivated influenza vaccines or SARS-CoV-2 vaccines]) are not allowed within 2 weeks of dosing and while on study is prohibited.
6. Any clinically significant illness, medical/surgical procedure or trauma within 4 weeks of the first administration of study treatment or planned surgical procedure during the study period.
7. Blood donation/blood loss greater than 500 mL during the 56 days prior to screening.
8. Any positive result at the Screening Visit for serum hepatitis B surface antigen (HBsAg), hepatitis C virus (HCV) antibody, and human immunodeficiency virus (HIV).
9. Abnormal vital signs, after at least 5 minutes remaining in the supine position at the Screening Visit and on Admission/Day -1, defined as any of the following:
 - Systolic blood pressure $>145 \text{ mmHg}$
 - Diastolic blood pressure $>95 \text{ mmHg}$
 - Heart rate <45 or $>100 \text{ bpm}$
10. Any clinically significant abnormalities in rhythm, conduction or morphology of the resting ECG, and any clinically important abnormalities in the 12-lead ECG as considered by the Investigator that may interfere with the interpretation of QTc interval changes.
11. Prolonged Fridericia QTcF $>450 \text{ msec}$ in males or $>470 \text{ msec}$ in females or shortened QTcF $<340 \text{ msec}$ or family history of long QT syndrome at the Screening Visit and on Admission/Day -1
12. ALT and/or AST $>1.0 \times \text{ULN}$ at the Screening Visit and on Admission/Day -1.
13. Current smokers, or those who have smoked or used nicotine products (including nicotine patches) within 1 month prior to dose administration (see [Section 5.3.2](#) for additional details).
14. History of alcohol abuse or excessive intake of alcohol as defined in [Section 5.3.2](#).

15. Positive screen for drugs of abuse or cotinine at the Screening Visit or admission to the study site CRU or positive screen for alcohol on admission to the study site CRU prior to the first administration of study treatment (see [Table 6](#)).
16. Positive test results for coronavirus disease 2019 (COVID-19) performed at admission to the CRU.
17. History of severe allergy/hypersensitivity/anaphylaxis or ongoing clinically important allergy/hypersensitivity, as judged by the Investigator or history of hypersensitivity to any components in the study treatment.
18. Excessive intake of caffeine containing drinks or food (more than 6 cups of coffee or equivalent per day) (see [Section 5.3.2](#) for definition of excessive).
19. Treatment with prescription or nonprescription medications (including over-the-counter [OTC] medications, supplements, and herbal preparations such as St. John's Wort extract) within 14 days prior to start of study treatment, unless in the opinion of an Investigator and Sponsor the medication will not interfere with the study. See [Section 6.6](#) for additional details.
20. Has received an Investigational Product within 30 days or a biologic within 90 days (or 5 half-lives for both, whichever is longer) prior to screening.
21. Consumption of poppy seeds, red wine, Seville oranges, Seville orange marmalade, grapefruit, or grapefruit juice, pomelos, exotic citrus fruits, grapefruit hybrids, or fruit juices within the 7 days prior to Admission/Day –1 (see Section 5.3.1).
22. Previous randomization to treatment in the present study.
23. Involvement in the planning and/or conduct of the study (applies to the Sponsor, contract research organizations, and study site staff, etc.).
24. Participants who are unlikely to cooperate with the requirements of the study.
25. Judgment by the Investigator that the participant should not participate in the study if they have any ongoing or recent (i.e., during the screening period) minor medical complaints that may interfere with the interpretation of study data or are considered unlikely to comply with study procedures, restrictions and requirements.

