Abbreviations: AE = adverse event; A_e = amount; AUC = area under the concentration versus time curve; AUC_(0-inf) = AUC from time zero extrapolated to infinity; AUC_(0-last) = AUC from time zero to the last quantifiable concentration; C_{EOI} = concentration at the end of 10-minute IV infusion; CL = systematic clearance; CL_r = renal clearance; C_{max} = maximum concentration; ECG = electrocardiogram; f_e = fraction; IV = intravenous; λ_z = elimination rate constant; PK = pharmacokinetics; t_{1/2} = half-life; QTcF = QT corrected for heart rate by Fridericia's formula; t_{max} = time to C_{max}; V_{ss} = volume of distribution at steady-state following intravenous dosing; V_z = volume of distribution following intravenous dosing.

Overall Design:

CS-1103-01 is a Phase 1a, single center, double-blind, placebo-controlled, randomized, single ascending-dose first in-human (FIH) study. All participants will be screened within 28 days of dose administration and participants will check-in to the inpatient clinical research unit (CRU) on their Admission/Day -1. Participants will be randomized on Day -1, the day prior to dosing, after meeting all eligibility criteria. Participants are scheduled to remain in the CRU for up to 48 hours postdose for safety and PK assessments.

Number of Participants:

Up to 40 healthy participants, aged 18 to 55 years will be randomized.

Intervention Cohorts and Duration:

Up to 5 cohorts of 8 participants (6 active, 2 placebo participants per cohort) will be enrolled with each participant assigned to receive a single dose of CS-1103 or placebo on 1 occasion (Day 1). Note: The dose will be capped at 3000 mg.

- Cohort 1: Dose level 1 (CS-1103 2.7 mg/kg, [REDACTED] or placebo [REDACTED])
- Cohort 2: Dose level 2 (CS-1103 8.0 mg/kg, [REDACTED] or placebo [REDACTED])
- Cohort 3: Dose level 3 (CS-1103 16.0 mg/kg, [REDACTED] or placebo [REDACTED])
- Cohort 4: Dose level 4 (CS-1103 26.7 mg/kg, [REDACTED] or placebo [REDACTED])
- Cohort 5: Dose level 5 (CS-1103 40.0 mg/kg, [REDACTED] or placebo [REDACTED])

The study duration will be approximately 37 days.

- Screening Period: up to 28 days
- CRU confinement period: 4 days
 - Treatment administration: 1 day
- CRU discharge through follow-up/end of study period: 5 days

Statistical Methods:

Descriptive statistics will be used as applicable to summarize the study data unless otherwise specified. Continuous variables: Sample size (n), mean, standard deviation (SD), median,

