4.0 STUDY DESIGN

4.1 Overall Design

This is a Phase 1a, single center, double-blind, placebo-controlled, randomized, single ascending-dose first-in-human (FIH) study. The study will recruit up to 40 healthy normal participants, aged 18 to 55 years inclusive, with standard inclusion/exclusion criteria for healthy participant studies. Up to 5 cohorts of 8 participants (6 active, 2 placebo participants per cohort) will be enrolled with each participant assigned to receive a single dose of CS-1103 or placebo on 1 occasion (Day 1).

All participants will be screened within 28 days of dose administration and participants will check-in to the inpatient clinical research unit (CRU) on Admission/Day –1. Participants will be randomized on Day –1, the day prior to their schedule CS-1103 administration (after meeting all eligibility criteria). Participants are scheduled to remain in the CRU for up to 48 hours postdose for safety and PK assessments. Participants will be discharged on Day 3 after completion of all scheduled assessments and will be asked to return to the CRU on Day 8 for the end of study (EOS) visit. Note: Discharge from the CRU may be delayed for up to 8 hours to optimize PK assessment (see [Section 8.4.1](#)). The study duration will be approximately 37 days.

All participants for a dose level may check-in to the CRU on the same date. However, each dose level will include 2 sentinel participants (1 active, 1 placebo) who will be dosed first and monitored by an Investigator for a minimum of 24 hours. The available safety and tolerability data from the sentinel participants, up to 24 hours post dose, will be reviewed by an Investigator. Following this safety data review, dosing of the remaining participants in the cohort may proceed (see [Section 10.1.7.1](#)). The remaining participants for each dose level will be randomized the day prior to dosing and will dose on Day 1, provided there are no safety or tolerability concerns, using a 5:1 randomization ratio to active or placebo study treatment separately for each dose level. A randomization list will be prepared for each cohort. See [Section 4.5](#) for dose escalation details.

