5.3.3 Activity

- Participants should refrain from strenuous exercise for 72 hours before the screening medical examination, 72 hours before admission, and throughout the residential period in the CRU and again 72 hours before the scheduled Follow-up/EOS Visit.
- Participants will be advised not to donate blood or plasma for at least 3 months after the last dose administration.
- Participants will be asked to remain in the supine position during dose administration and for at least 40 minutes post-EOI
- On days when digital ECG (dECG) Holter measurements are being taken, study participants should be restricted to a low level of physical activity and should refrain from any activities likely to stimulate or excite them (e.g., video games, stimulating movies, or television shows, etc.) during extraction timepoints. Additionally, participants should

refrain from using hand-held electronic or electrical devices (e.g., cell phones, hair dryers, etc.) as these have a potential to interfere with ECG signals.

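### Exclusions 7 and 20 count back from screening, and other criteria cover the up to 28 days between screening and dosing only in part

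*Protocol*

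**What the plan says.** Two look-back criteria in Protocol Section 5.2 end at screening.

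- Exclusion 7: "Blood donation/blood loss greater than 500 mL during the 56 days prior to screening".
- Exclusion 20 sets 30 days for an investigational product; for a biologic the look-back reads "within 90 days (or 5 half-lives for both, whichever is longer) prior to screening".

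Screening and dosing can be four weeks apart. Section 4.1 states: "All participants will be screened within 28 days of dose administration". Table 1 places screening between Day -28 and Day -2. Eligibility is settled later, because the Synopsis states: "Participants will be randomized on Day -1, the day prior to dosing, after meeting all eligibility criteria". Table 1 accordingly schedules the inclusion/exclusion check at both Screening and Admission.

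Other look-back criteria in the same list (4, 5, 6, 13 and 19) run up to dosing. Two of them bear on this point:

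- Exclusion 6: "Any clinically significant illness, medical/surgical procedure or trauma within 4 weeks of the first administration of study treatment".
- Exclusion 19, on prescription and nonprescription medication: "within 14 days prior to start of study treatment, unless in the opinion of an Investigator and Sponsor" judge that it will not interfere. Section 6.6 repeats the 14-day abstention with the same exception.

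Outside exclusion 7, the only rule on donation is in Section 5.3.3: "Participants will be advised not to donate blood or plasma for at least 3 months after the last dose administration".

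**The concern.** A washout rule is meant to keep recent exposure out. Exclusions 7 and 20 reach back from screening and stop there, so they act on remote events and not on more recent ones. Checking them again at Admission gives the same answer as at screening, because the wording still looks only at the time before screening.

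At stake is the cleanness of small groups in a first-in-human study. Each dose level has 6 active participants, so one person carrying the effect of another trial product or a recent large donation is 1/6, or about 17%, of that level's active data on adverse events, laboratory values and PK. No hypothesis test is planned, so error rates are not affected. The matter is how well each dose group can be described.

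**Working it through.** **Inputs**

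| Item | Value | Source |
|---|---|---|
| Screening | Day -28 to Day -2 | Protocol Table 1 |
| Exclusion 7 look-back | 56 days before screening | Section 5.2 |
| Exclusion 20 look-back | 30 days (investigational product) or 90 days (biologic) before screening, or 5 half-lives if longer | Section 5.2 |
| Exclusion 6 look-back | 4 weeks = 28 days before dosing | Section 5.2 |
| Exclusion 19 look-back | 14 days before dosing, with an exception | Sections 5.2 and 6.6 |
| Day numbering | no Day 0 | SAP Section 6.4 |

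The plan gives no figure for this gap. As a check on the timeline, 28 (screening) + 4 (confinement) + 5 (follow-up) = 37 days, which matches the stated study duration.

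**Step 1: what exclusions 7 and 20 cover.** With no Day 0, a participant screened on Day -d is screened d days before dosing. A look-back of L days then covers d to d + L days before dosing and leaves the last d days uncovered. For exclusion 20, L is taken as 30 or 90; a 5-half-life rule would lengthen the far end only.

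| Screened on | Uncovered by 7 and 20 | Exclusion 7 covers | Exclusion 20, product | Exclusion 20, biologic |
|---|---|---|---|---|
| Day -28 | last 28 days | 28 to 84 days before dosing | 28 to 58 | 28 to 118 |
| Day -21 | last 21 days | 21 to 77 | 21 to 51 | 21 to 111 |
| Day -14 | last 14 days | 14 to 70 | 14 to 44 | 14 to 104 |
| Day -2 | last 2 days | 2 to 58 | 2 to 32 | 2 to 92 |

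For someone screened on Day -28, a donation above 500 mL made 80 days before dosing excludes, while one made 5 days before dosing does not meet exclusion 7. An investigational product taken 55 days before dosing excludes; one taken 20 days before dosing does not meet exclusion 20, and it also lies outside the 14 days of exclusion 19.

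**Step 2: what the dosing-anchored criteria add.**

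- *Blood loss through illness, a procedure or trauma.* Exclusion 6 spans 28 days, so the open time is 28 - 28 = 0 days.
- *Voluntary donation above 500 mL.* Exclusion 6 does not clearly apply. Unless donation is read as a medical procedure, up to 28 days stay open. The advice in Section 5.3.3 begins only after dosing.
- *Investigational product or biologic.* If exclusion 19 includes trial products, the open time is max(0, d - 14): 14 days for screening on Day -28 (about Day -28 to Day -15), 7 days for Day -21, and none from Day -14 on. If it does not, all d days stay open, up to 28. The documents do not say which reading is meant.

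**Step 3: after the change.** With both criteria extended to dosing, the uncovered time falls from 2 to 28 days to 0. If they run only to Admission/Day -1, about 1 day remains, and the participant spends it confined in the research unit.

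**The case against.** The strongest reply is that the plan has several other safeguards.

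- Exclusion 6 fully covers blood loss from illness, a procedure or trauma, and exclusion 19 plausibly covers trial products in the last 14 days. This stands. A reader of exclusions 7 and 20 alone might infer that an event after screening excludes nobody, or that nothing else closes the gap. The documents do not support that.
- Hematology and chemistry are repeated at Admission, inclusion 7 requires the participant to be judged healthy on those results, and exclusions 3 and 12 set eGFR and ALT/AST limits then. This stands in part: these checks catch some effects, but none sets a rule on donation or trial products. Exclusion 25 concerns minor complaints and likely compliance, and exclusion 22 concerns this study only.
- Section 6.6 has medication within 1 month of dosing recorded. That is true, but recording does not exclude.
- Change from baseline uses the last value before dosing (SAP Section 6.5), so an earlier fall in hemoglobin is largely in the baseline already. This is fair and limits the effect on laboratory summaries.

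Two further inferences are tempting and should not be drawn.

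- *Total blood volume.* Adding 500 mL to the study maximum of 450 mL gives 950 mL, but this does not measure the gap. Exclusion 7 bars only losses above 500 mL, so a donation of exactly 500 mL in the gap would still be allowed after the change. The 450 mL (Section 8.0) is also a ceiling that includes any extra assessments.
- *Stopping escalation.* The adverse event rules in Section 4.6.1 require at least possible relatedness, and the moderate-event rule needs two participants. Section 10.3 presumes an SAE possibly related unless another explanation is obvious, but it also has the investigator weigh alternative causes. Nothing in the documents shows a route from a pre-dose donation or trial product to a stop.

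**Conclusion.** The point holds in a limited form. Exclusions 7 and 20 do not themselves cover the up to 28 days between screening and dosing, and exclusions 6 and 19, with Section 6.6, close that period only in part. Two gaps remain: a voluntary donation above 500 mL, for up to 28 days; and an investigational product or biologic, for up to 14 or up to 28 days depending on how exclusion 19 is read. Even on the narrower reading, 14 days with an opinion-based exception is a weaker bar than the 30 days, 90 days or 5 half-lives that exclusion 20 sets without exception.

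This rests on three assumptions: that screening means the date of the Screening Visit, that a donation is not a medical procedure under exclusion 6, and that the investigator applies the criteria as worded. The documents give no frequency. It is probably low, so this is a minor improvement and no threat to the study's conclusions.

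**What to change.** Add to exclusions 7 and 20 the words *or between screening and study treatment administration*, and apply them at the existing Admission/Day -1 eligibility check. Start the donation advice in Section 5.3.3 at screening.

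The alternative is to anchor both criteria to study treatment administration, as in exclusions 4, 5, 6, 13 and 19. It also closes the gap, but it shortens the far end. For screening on Day -28, exclusion 20 now reaches back 28 + 30 = 58 days before dosing for an investigational product and would then reach back 30. The added clause keeps the present reach, so nobody excluded now becomes eligible. Which to use is for the sponsor to decide.

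The cost is a few words in the next amendment and a question at a check that already takes place. The downside is that a rare participant becomes ineligible at Admission.

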5.3 Lifestyle Considerations

5.3.1 Meals and Dietary Restrictions

- Refrain from consumption of poppy seeds, red wine, Seville oranges, Seville orange marmalade, grapefruit, or grapefruit juice, pomelos, exotic citrus fruits, grapefruit hybrids, or fruit juices from 7 days prior to Admission/Day –1 and through the duration of the study (see [Section 5.2](#), exclusion criteria 21).
- At least a 10 hour overnight fast (with water ad libitum) is required prior to study treatment administration and a 4 hour fast is required following study treatment administration

- Participants will be asked to drink 360 mL of water after completion of their final predose urine void. After that no water is allowed until 1 hour after dose administration, after which time, water is allowed ad libitum. At 2 hours postdose, participants will be encouraged to drink another 360 mL of water. Participants are encouraged to drink at least 1 L of water over the first 12 hours post drug administration (inclusive of the 2 × 360 mL of water specified above). If participants are unable to drink the complete 360 mL of water, the reason why and the exact amount consumed will be documented.

5.3.2 Caffeine, Alcohol, and Tobacco

- Participants will abstain from ingesting excessive caffeine- or xanthine-containing products (e.g., coffee, tea, red bull, cola drinks, and chocolate [more than 6 cups of coffee or equivalent per day]) within 7 days prior to study treatment administration and through the final Follow-up/EOS Visit
 - One caffeine unit is contained in the following items: 1 (6 oz) cup of coffee, 2 (12 oz) cans of cola, 1 (12 oz) cup of tea, $\frac{1}{2}$ (4 oz) cup of energy drink (e.g., Red Bull), or 3 (1 oz) chocolate bars
- Participants will abstain from alcohol intake 48 hours prior to study treatment administration and until after the final Follow-up/EOS Visit. History of alcohol abuse or excessive intake of alcohol defined as:
 - an average weekly intake of >14 drinks/week for men or >7 drinks/week for women. One drink is equivalent to (12 g alcohol) = 5 ounces (150 mL) of wine or 12 ounces (360 mL) of beer or 1.5 ounces (45 mL) of 80 proof distilled spirits
- Use of tobacco products will not be allowed within 1 month prior to study treatment administration and through the final Follow-up/EOS Visit.

